Appendix A.	Reference Values/Toxicity Grades	39
CCI		
Appendix C.	Calculation of eDiary Efficacy Endpoints	51

Table of Abbreviations

In addition to the study glossaries and abbreviations defined in the protocol, here is a table of abbreviations used in this document:

Abbreviation	Definition
AE	Adverse event
ANC	Absolute neutrophil count
ALT	Alanine aminotransferase
AST	Aspartate aminotransferase
C-SSRS	Columbia-Suicide Severity Rating Scale
CTCAE	Common Toxicity Criteria for Adverse Events
DBP	Diastolic blood pressure
DMP	Data management plan
DTP	Data transfer plan
EAS	Efficacy analysis set
ECG	Electrocardiogram
EDC	Electronic Data Capture
eDiary	Electronic diary
EOS	End of study
E-R	Exposure-Response
FAS	Full analysis set
GSO-DM	Global Study Operations-Data Management
IP	Investigational product
IPD	Important protocol deviation
IVR	Interactive Voice Response
MedDRA	Medical Dictionary for Regulatory Activities
MIDAS	Migraine Disability Assessment
MO	Medication overuse
MPFID	Migraine Physical Function Impact Diary
MSQ	Migraine-Specific Quality of Life Questionnaire
OLE	Open-label Extension
PD	Pharmacodynamics
PK	Pharmacokinetics
PRO	Patient reported outcome
PROMIS	Patient-Reported Outcomes Measurement Information System

Abbreviation	Definition
QM	Dosed monthly
SAP	Statistical analysis plan
SBP	Systolic blood pressure
SAS	Safety analysis set
SD	Standard deviation
SSAP	Supplemental statistical analysis plan
TEAE	Treatment emergent adverse event
ULN	Upper limit of normal
WHODRUG	World Health Organization Drug Dictionary

1. Introduction

The purpose of this Statistical Analysis Plan (SAP) is to provide details of the statistical analyses that have been outlined within the **Protocol Amendment 3 for Study 20130255 AMG 334, dated 31 March 2016**. The scope of this plan includes the final analysis that is planned and will be executed by the Biostatistics department unless otherwise specified. **For the CHU substudy, please refer to the CHU substudy SAP.**

2. Objectives

Primary

To characterize the safety and tolerability of long-term administration of AMG 334

Secondary

To characterize the efficacy of long-term administration of AMG 334 as assessed by:

- Change from baseline in monthly migraine days
- Proportion of subjects with at least 50% reduction from baseline in monthly migraine days
- Change from baseline in monthly acute migraine-specific medication treatment days
- **Change from baseline in monthly cumulative hours of headache**

Exploratory

- **To evaluate the effect of AMG 334 as measured by reduction from baseline in monthly migraine attacks, in subjects with chronic migraine**
- To evaluate the effect of AMG 334 as measured by the reduction from baseline in
 - monthly headache (migraine and non-migraine headache) days
 - headache days with moderate or severe intensity
 - monthly average severity of migraine pain
- To evaluate the effect of AMG 334 as measured by the change from baseline in monthly average severity of migraine related symptoms (nausea, vomiting, phonophobia and photophobia) for qualified migraine headaches
- To evaluate the effect of AMG 334 on
 - migraine-specific quality of life as measured by the Migraine-Specific Quality of Life Questionnaire (MSQ), version 2.1
 - migraine-related disability, as measured by the Migraine Disability Assessment (MIDAS)
 - pain interference with daily activities and migraine-specific impact, as measured by the Patient-Reported Outcomes Measurement Information System (PROMIS) Pain Interference Scale short form and single pain and migraine symptom interference questions

- To evaluate effect of AMG 334 on change in physical impairment over time as measured by the Migraine Physical Function Impact Diary (MPFID).
- To evaluate the effect of AMG 334 on change in impact on everyday activities over time as measured by the MPFID
- To evaluate AMG 334 pharmacokinetic (PK) in subjects with migraine
- To investigate potential biomarker development by analysis of blood samples

3. Study Overview

3.1 Study Design

This is a multicenter, open-label study designed to assess the long-term safety and efficacy of AMG 334. Subjects who complete the 12-week double-blind treatment phase (DBTP) of the AMG 334 20120295 parent study and meet all AMG 334 20130255 eligibility criteria will be enrolled into the study. Enrollment should occur within 14 days after the parent study's week 12 visit. **Subjects who enroll in the AMG 334 20130255 study will end the AMG 334 20120295 study and will not participate in the parent study safety follow-up visit.**

All subjects who have enrolled in the study under Protocol Amendment 3 or later, will receive open-label AMG 334 140 mg every month (QM) SC for 13 months. Subjects who enrolled in the 20130255 study, prior to Protocol Amendment 3, will increase the open-label dose from 70 mg QM to 140 mg QM at the first available opportunity at either week 4, 8, 12, 16, 20, 24, or 28 visits. Subjects who have already completed the week 28 visit will continue to receive 70 mg QM.

All subjects will receive open-label AMG 334 QM SC for 13 months followed by a 12-week safety follow up visit (16 weeks after the last dose of investigational product [IP]).

Investigational product AMG 334 70 mg or 140 mg will be dosed QM, SC.

3.2 Sample Size

All subjects who completed the 12-week DBTP of the parent study, meet the inclusion and exclusion criteria for the 20130255 OLE study, and consent to receive IP will be eligible to be enrolled. Up to **651** subjects may participate in the study.

4. Study Endpoints and Covariates

4.1 Study Endpoints

Primary Endpoint

The primary endpoint for the study is subject incidence of adverse events.

Secondary Endpoints

- change from baseline in monthly migraine days at assessment time points
- achievement of at least a 50% reduction from baseline in monthly migraine days at assessment time points
- **change from baseline in monthly acute migraine-specific medication treatment days at assessment time points**
- **change from baseline in cumulative monthly headache hours at assessment time points**

Exploratory Endpoints

Change from baseline in

- monthly migraine attacks at assessment time points
- monthly headache (migraine and non-migraine headache) days at assessment time points
- monthly moderate and severe headache (migraine and non-migraine headache) days at assessment time points
- monthly average severity of migraine pain at assessment time points
- monthly average severity of migraine related symptoms (nausea, vomiting, phonophobia, photophobia) for qualified migraine headaches at assessment time points
- migraine-specific quality of life, as measured by the MSQ, version 2.1 at assessment time points
- migraine-related disability, as measured by the MIDAS at assessment time points
- pain interference with daily activities and migraine-specific impact, as measured by the PROMIS Pain Interference Scale short form and single pain and migraine symptom interference questions at assessment time points
- **change in physical impairment over time as measured by the MPFID**
- **change in impact on everyday activities over time as measured by the MPFID**
- AMG 334 pharmacokinetic (PK) concentration
- monthly acute medication use at assessment time points

4.2 Planned Covariates

There are no planned covariate analyses.

Region (North America vs. Other) and medication overuse (Yes vs. No) as collected on the eCRF in the parent study 20120295, if available, and if not available as collected per the parent study randomization stratification factors may be used for subgroup analysis of the appropriate endpoints.

5. Hypotheses and/or Estimations

This is a single-arm estimation study. No hypotheses will be tested.

6. Definitions

6.1 Definition of Terms Included in Study Endpoints

6.1.1 Safety Endpoints

Serious Adverse Event (SAE)

SAEs determined by the flag indicating if the adverse event is serious on the Adverse Events (AE) eCRF page will include those that occur after signing of the informed consent and up to and including end of study.

Treatment-Emergent Adverse Event

Adverse Events (AEs) recorded on the Adverse Events eCRF page that occur on or after first dose of investigational product as determined by the flag indicating if the adverse event started prior to the first dose on the Adverse Events eCRF and up to and including 112 days after the end of investigational product (16 weeks after the last dose of IP) or end of study, whichever comes earlier.

An AE that started in parent study 20120295 is only considered treatment emergent in the OLE study 20130255 if there is a worsening of the event. If the event is ongoing with no changes in severity, then it will not be considered an AE in 20130255.

Treatment-Related Adverse Event

A treatment-related AE is defined as a treatment-emergent adverse event that is considered by investigators to have reasonable possibility that it may have been caused by IP as determined by the flag indicating if the event is caused by investigational product on the Adverse Events eCRF page.

Columbia-Suicide Severity Rating Scale (C-SSRS)

The C-SSRS is a clinician rating of suicidal behavior and ideation. The version "Since Last Visit" will be used for this study. The C-SSRS consists of a maximum of 20 items to evaluate suicidal behavior and suicidal ideation. Please refer to [Appendix B](#) for more details.

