9. SAFETY DATA COLLECTION, RECORDING, AND REPORTING

9.1 Adverse Events

9.1.1 Definition of Adverse Events

An adverse event is defined as any untoward medical occurrence in a clinical trial subject. The event does not necessarily have a causal relationship with study treatment. The investigator is responsible for ensuring that any adverse events observed by the investigator or reported by the subject are recorded in the subject's medical record.

The definition of adverse events includes worsening of a pre-existing medical condition. Worsening indicates that the pre-existing medical condition **or underlying disease** (eg, diabetes, migraine headaches, gout) has increased in severity, frequency, and/or duration **more than would be expected**, and/or has an association with a significantly worse outcome **than expected**. A pre-existing condition that has not worsened **more than anticipated (ie, more than usual fluctuation of disease)** during the study or involves an intervention such as elective cosmetic surgery or a medical procedure while on study, is not considered an adverse event.

An adverse device effect (ADE) is any adverse event related to the use of a medical device. Adverse device effects include adverse events resulting from insufficient or inadequate instructions for use, adverse events resulting from any malfunction of the device, or adverse events resulting from use error or from intentional misuse of the device.

The investigator's clinical judgment is used to determine whether a subject is to be removed from treatment due to an adverse event. In the event a subject, or subject's legally acceptable representative requests to withdraw from protocol-required therapies or the study due to an adverse event, refer to [Section 8.1](#) for additional instructions on the procedures recommended for safe withdrawal from protocol-required therapies or the study.

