9.2 Reporting of Adverse Events

9.2.1 Reporting Procedures for Adverse Events That do not Meet Serious Criteria

The investigator is responsible for ensuring that all adverse events observed by the investigator or reported by the subject that occur after first dose of investigational product through the end of study are reported using the applicable CRF (eg, Adverse Event Summary), including events that are reported to the Event Adjudication Committee for adjudication.

The investigator must assign the following adverse event attributes:

- Adverse event diagnosis or syndrome(s), if known (if not known, signs or symptoms),
- Dates of onset and resolution (if resolved),
- Severity,
- Assessment of relatedness to investigational product **and/or any study-mandated activity or procedure**, and
- Action taken.

The adverse event grading scale used will be the Common Terminology Criteria for Adverse Events (CTCAE). The grading scale used in this study is described in [Appendix A](#). The criteria for grade 4 in the CTCAE grading scale differs from the regulatory criteria for serious adverse events. It is left to the investigator's judgment to report these grade 4 abnormalities as serious adverse events.

If the severity of an adverse event changes from the date of onset to the date of resolution, record as a new event on the Adverse Event Summary CRF.

The investigator must assess whether the adverse event is possibly related to the investigational product. This relationship is indicated by a "yes" or "no" response to the question: "Is there a reasonable possibility that the event may have been caused by the investigational product?"

During the CHU, the investigator must assess whether the adverse event is possibly related to the IP and/or device. This relationship is indicated by a "yes" or "no" response to the question: Is there a reasonable possibility that the event may have been caused by the IP. The investigator must assess whether the adverse event is possibly related to the PFS or **prefilled** AI/pen used to administer IP. The relationship is indicated by a

“yes” or “no” response to the question: Is there a reasonable possibility that the event may have been caused by the device?

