14. APPENDICES

Appendix A. Additional Safety Assessment Information

Adverse Event Grading Scale

The Common Terminology Criteria for Adverse Events Version 4 (CTCAE v4) is available at the following location:

http://ctep.cancer.gov/protocolDevelopment/electronic_applications/ctc.htm

Grade	Clinical Description
1	Mild; asymptomatic or mild symptoms; clinical or diagnostic observations only; intervention not indicated
2	Moderate; minimal, local or noninvasive intervention indicated; limiting age-appropriate instrumental ADL*
3	Severe or medically significant but not immediately life-threatening; hospitalization or prolongation of hospitalization indicated; disabling; limiting self care ADL**
4	Life-threatening consequences; urgent intervention indicated
5	Death related to AE

A semi-colon indicates 'or' within the description of the grade.

Activities of Daily Living (ADL):

* Instrumental ADL refer to preparing meals, shopping for groceries or clothes, using the telephone, managing money, etc.

** Self care ADL refer to bathing, dressing and undressing, feeding self, using the toilet, taking medications, and not bedridden.

Drug-induced Liver Injury Reporting and Additional Assessments

Reporting

To facilitate appropriate monitoring for signals of DILI, cases of concurrent AST or ALT and TBL and/or INR elevation according to the criteria specified in [Section 6.3](#) require the following:

- The event is to be reported to Amgen as a serious adverse event within 24 hours of discovery or notification of the event (ie, before additional etiologic investigations have been concluded)
- The appropriate CRF (eg, Adverse Event CRF) that captures information necessary to facilitate the evaluation of treatment-emergent liver abnormalities is to be completed and sent to the Amgen.

Other events of hepatotoxicity and potential DILI are to be reported as serious adverse events if they meet the criteria for a serious adverse event defined in [Section 9.2.2](#).

Additional Clinical Assessments and Observation

All subjects in whom investigational product(s) or protocol-required therapies is/are withheld (either permanently or conditionally) due to potential DILI as specified in

Sections 6.3.1 and 6.3.2 or who experience AST or ALT elevations $>3 \times$ ULN are to undergo a period of “close observation” until abnormalities return to normal or to the subject’s baseline levels. Assessments that are to be performed during this period include:

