10.6.1 Adverse Events and Disease Related Events

The Medical Dictionary for Regulatory Activities (MedDRA) version **18.0** or later will be used to code all events categorized as adverse events (AEs) to a system organ class and a preferred term (PT). **All adverse events will be graded using the Common Terminology Criteria for Adverse Events (CTCAE) Version 4.** Refer to [Section 6.1](#) for the definition of treatment-emergent adverse event.

Exposure-adjusted subject incidence of AEs will be summarized for all treatment-emergent AEs (TEAEs), serious AEs, AEs leading to withdrawal of investigational product, fatal AEs and treatment-related adverse events.

Exposure-adjusted subject incidence of all TEAEs, serious AEs, AEs leading to withdrawal of investigational product, serious AEs leading to withdrawal of investigational product and fatal AEs will be tabulated by system organ class and preferred term in alphabetical order.

In addition, exposure-adjusted subject incidence of all TEAEs and serious AEs will be tabulated by system organ class, preferred term and CTCAE grade in alphabetical order. Exposure-adjusted subject incidence of all TE AEs and serious AEs will also be tabulated by preferred term in descending order of frequency.

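### Under SAP 6.1.1, a parent-study AE that leads to stopping product at an unchanged grade can be missing from the extension's withdrawal and treatment-related AE tables, and a few newly serious carry-over events may be missed too

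*SAP*

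**What the plan says.** "The primary endpoint for the study is subject incidence of adverse events" (SAP 4.1), and the primary objective is long-term safety and tolerability.

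SAP 6.1.1 handles carry-over events in two adjacent sentences. The first says that an AE with onset in the parent study "is only considered treatment emergent in the OLE study 20130255 if there is a worsening of the event". The second says: "If the event is ongoing with no changes in severity, then it will not be considered an AE in 20130255". The SAP does not define worsening.

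The same section defines serious AEs separately. They are identified by the serious flag on the AE eCRF page and "will include those that occur after signing of the informed consent and up to and including end of study". It defines treatment-related AEs as a subset of the treatment-emergent ones.

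SAP 10.6.1 plans exposure-adjusted incidence for all treatment-emergent AEs, serious AEs, "AEs leading to withdrawal of investigational product", fatal AEs and treatment-related AEs. SAP 10.2 separately tabulates withdrawals from product with their reasons.

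Protocol 9.1.1 uses worsening more broadly, for a pre-existing condition. The condition has worsened if it "has increased in severity, frequency, and/or duration" beyond expectation, or is tied to a significantly worse outcome. Protocol 9.2.1 gives the recording rule: "If the severity of an adverse event changes from the date of onset to the date of resolution, record as a new event".

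**The concern.** The second sentence turns on severity alone, and it is not confined to treatment-emergent status: it says the event is not an AE in this study at all. The clearest casualty is an event that was tolerable at parent week 12, persists at the same grade, and eventually makes the subject stop product. That is a failure of long-term tolerability, which is what the extension is meant to characterise. A literal programmer would drop it from the withdrawal table. It would also drop out of the treatment-related table, which draws only on treatment-emergent events.

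A smaller gap concerns seriousness. A carry-over event can become serious without a change of grade, and the SAP does not say whether the serious-AE definition or the carry-over sentence then decides. Enrolled subjects skip the parent safety follow-up visit (SAP 3.1), so the extension is where such changes would be seen.

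Each omission runs in the same direction, towards a more favourable safety profile.

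**Working it through.** The plan states no figure on this point. The 651 subjects are an upper limit with no precision statement behind it, so there is nothing to reproduce. The check is a trace of what happens to a parent-onset event, followed by a sizing on stated assumptions.

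**Trace under the current text**

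1. *The grade rises.* Protocol 9.2.1 requires a new record. It has its own onset in the extension and meets the treatment-emergent definition. Captured.
2. *It becomes serious and the grade rises.* In Protocol Appendix A, grade 3 includes "hospitalization or prolongation of hospitalization indicated", grade 4 is life-threatening and grade 5 is death. Becoming serious on those criteria usually moves the grade, so this reduces to case 1. Captured.
3. *It becomes serious and the grade does not change.* This can happen if the event was already grade 3, or is serious only under the medical-importance criterion of Protocol 9.1.2. No new record is required. Extension screening cannot begin until parent week-12 procedures are complete (Protocol 5), so onset usually precedes extension consent. The serious-AE definition has no treatment-emergent condition, but it takes events occurring after consent. Unclear.
4. *Product is withdrawn because of it and the grade does not change.* No new record is required, onset stays before the first extension dose, and the second carry-over sentence excludes it. Missing on a literal reading. Disposition shows the stop, but not the event by preferred term.
5. *It becomes more frequent at the same grade.* Captured only if the investigator records the worsening as a new AE in the sense of Protocol 9.1.1.

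The rate in SAP 10.6.1.1 also needs a time of occurrence within a dose level. The SAP gives none for cases 3 to 5 where no new record exists.

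**Size, by assumption**

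Input from the documents: N = 651 (Protocol 10.2, SAP 3.2). Assumed, with no source in the documents:
- a, share of subjects entering with an ongoing parent AE: 5–20%
- b, share of those whose event worsens without a grade change: 2–10%
- c, share of those with no other treatment-emergent AE: 30–100%

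Subjects affected = N × a × b. Loss from any-AE incidence in percentage points = 100 × a × b × c. The factor c is needed because a subject with another treatment-emergent AE is still counted.

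- Low: 651 × 0.05 × 0.02 = 0.7 subjects; 100 × 0.05 × 0.02 × 0.3 = 0.03 points.
- High: 651 × 0.20 × 0.10 = 13.0 subjects; 100 × 0.20 × 0.10 × 1.0 = 2.0 points.
- One subject is 100/651 = 0.15 points.

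For the withdrawal table, assume 2–5% of subjects stop for an AE: 651 × 0.02 = 13 and 651 × 0.05 = 33. Losing 1 of 33 removes 3% of the table; losing 3 of 13 removes 23%. The loss of 1 to 3 subjects is also an assumption.

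**The case against.** The strongest reply is that the first sentence already counts worsening, and the second only describes the unchanged case. Excluding unchanged carry-over events is what treatment-emergent means. This stands in part: the text is two sentences in tension, not one plain severity-only rule. But the SAP gives no way to apply a broader worsening, and the recording rule in Protocol 9.2.1 makes severity decisive in practice.

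Second, serious AEs have their own definition without a treatment-emergent condition, and seriousness usually brings a grade change. Exclusion criteria 201 and 202 also limit serious carry-over at entry. This stands, and leaves only case 3.

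Third, Protocol 9.1.1 speaks of pre-existing conditions, and an investigator may use it to record a more frequent event as a new AE. Moreover, every ongoing event gets longer, so a programmed duration test would make nearly all carry-over events treatment-emergent. Both points stand and shape the fix.

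Fourth, withdrawals and their reasons appear under SAP 10.2, and their timing and reasons under SAP 9.4, so the stop is not hidden. True, but that does not put the event in the AE tables. Nor can disposition stand in for them: the safety-concern reason in Protocol 8.3.1 also covers matters such as contraception failure and breast feeding. For the same reason, a mismatch between the two tables would not by itself show an error.

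**Conclusion.** The point holds in a limited form. On a literal reading, a same-grade carry-over AE that leads to withdrawal of product can be missing from the withdrawal and treatment-related AE tables, and nothing else in the documents restores it there. A same-grade carry-over AE that becomes serious may be missed, because the governing rule is not stated.

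Three stronger readings are tempting and not supported:
- A reader might infer that every carry-over AE is dropped unless its grade changes. The first sentence still counts worsening.
- A reader might infer that events which become serious are generally lost from the primary endpoint. Most change grade and become new records, and serious AEs are flagged separately.
- A reader might infer that the rule falls mainly on subjects who had AMG 334 in the parent study. Former placebo subjects can also enter with ongoing AEs, and the documents have no data on the split.

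The effect on overall AE incidence is probably small: 0.03 to 2.0 points under ranges that are wholly assumed. The withdrawal table could change by a larger fraction, also by assumption. The study tests no hypothesis, so the harm is a one-directional error in descriptive rates. It should be corrected because the affected tables bear directly on tolerability.

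**What to change.** Amend the second carry-over sentence of SAP 6.1.1. A parent-onset AE counts in 20130255 if, after the first extension dose, any of these occurs:
- its CTCAE grade increases, dated from the new-grade record;
- it becomes serious, dated from when it became serious;
- product is withdrawn because of it, dated from the end-of-IP date.

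State that this rule also decides entry into the serious, withdrawal and treatment-related tables. Specify an increase, because a fall in grade also produces a new record under Protocol 9.2.1. Worsening in frequency or duration beyond expectation should count only when the investigator records it as a new AE in the sense of Protocol 9.1.1; do not program a duration rule. List unchanged carry-over events separately.

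The cost is a short SAP edit and a derivation from the severity, serious-flag and action-taken fields. Two details need confirming. The date an event became serious is not among the attributes listed in Protocol 9.2.1, so its source must be named. Ongoing parent events must also be held on the extension AE page, which the prior-to-first-dose flag suggests is possible. The downside is a slightly higher reported incidence.
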